Study Protocol and Statistical Analysis Plan

Protocol Title: Depression Care to Improve Adherence to PMTCT Care Continuum and Pregnancy Outcomes

NCT03892915

Date: 4/16/19

Investigators:

1. [name], Makerere University, School of Public Health (Co-PI)
2. [name]; RAND Corporation (Co-PI)
3. [name]; Ministry of Health (Co-I)
4. [name], Makerere University, School of Medicine (Co-I)
5. [name]; Mulago Hospital (Co-I)
6. [name]; Mildmay Uganda (Co-I)

Brief outline of the rationale for the study

Depression is common among HIV+ pregnant women, in both prenatal and post natal phases and depression often impedes adherence to PMTCT care, parenting, and early child health development. Treating depression could mitigate these consequences and help ensure optimum pregnancy and maternal and child health outcomes. The proposed cluster randomized controlled trial will compare the effects of evidence-based depression care vs. usual care on adherence to each step of the PMTCT care continuum at 8 ANC clinics and with 400 HIV+ depressed pregnant women (50 per site). Four (4) clinics will implement usual care and 4 will implement usual care plus depression care [anti depressant therapy(ADT) and problem solving therapy (PST)]. Peer mothers will be trained to assist in depression screening and implement PST, while nurses will be trained to diagnose depression and provide ADT, under the supervision of psychiatric specialists. PST will be recommended for all women deemed eligible for treatment, while ADT will be recommended for only those with severe or refractory depression.

Primary aims of the study:

1. Integrate evidence-based PST and ADT into usual care, using the gold standard, stepped care approach.
2. Assess whether the integrated depression care model is superior to usual care on (1) adherence to each step of the PMTCT care continuum and maternal viral suppression (primary outcomes); (2) prevention of infant HIV infection, and maternal and child health outcomes (secondary outcomes), and 3) depression treatment uptake and depression alleviation (depression care processes).

Secondary aim;

Examine how (1) depression and (2) depression alleviation are associated with maternal viral load, adherence to each step of the PMTCT care continuum, and mother and child health outcomes; and identify potential mediators (e.g., HIV disclosure; stigma; problem solving skills) of these relationships.

Methods

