We will enroll all consenting eligible clients and survey them at baseline, month 6, 12 and 18 following delivery. For those who miscarry, a final survey will take place 6 months after the miscarriage to assess successful transition to receive HIV care at the HIV clinic. At all sites, HIV+ adult patients who are early enough in their gestation period to be eligible for the study will be informed of the study and screened for potential depression by trained peer mothers using the EPDS-2. The screening will take place in a private room and those who screen positive will receive depression psycho-education. Eligible women who express interest in participating in the study will be connected by the peer mother to the study coordinator (via phone if the coordinator is not at the clinic that day) so that the coordinator can describe the study in detail, confirm eligibility and obtain written consent; these procedures are done during the same clinic visit, or the next day that the coordinator is at the clinic.

Qualitative data will be collected from peer mothers and midwife nurses at baseline, 12 and 24 months, at the intervention sites to assess: successes and challenges in screening, diagnosing and treating patients for depression; the training and supervision process; and impact of depression and its treatment on pregnancy and PMTCT care, clinic functioning, and provider job satisfaction and burnout. We will also interview 40 client participants (20 clinically depressed who were treated, and 20 not treated) at their final study assessment to assess their experiences with pregnancy.

Data analysis

Statistical Analysis. We will first compare clinic-level differences, using standard t-tests or, where the observations per clinic vary, t-tests weighted by cluster-size. Like most cluster RCTs, we do not have the 20+ clusters needed to reliably adjust standard errors for clustering, so we will use the conventional approach of using regression methods on individual level data for most analyses, but will conduct sensitivity analyses using a range of plausible ICC values for the outcomes.

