Primary Aim 1: intervention effects on primary outcomes. We will use logistic regression to test for differences between the two study arms on (i) PMTCT adherence, coded as a binary variable, at each stage of the PMTCT care continuum, and (ii) maternal viral suppression. The regression models will include patient characteristics such as age, CD4 and HIV disclosure status that may explain variance in observed differences. We will also explore significant interactions between the covariates and study arm to assess which patient types are likely to be adherent and virally suppressed in depression care vs. usual care. The effect of depression care on PMTCT adherence will be examined using intention to treat as the primary approach. We will use a repeated-measures model that will allow us to incorporate correlation in measurements of each person over time. The sample size of individuals for such models is adequate. The model formulation is: $\text{adherence}_{it} = \alpha + \beta G_i + \gamma(t) + \delta G_i \times t + \theta_i + \varepsilon_{it}$ where i is individual, t is continuous time, G is binary indicator of treatment group, β allows for baseline differences between the two groups, γ is the time trend in the outcome common to both groups, and δ is the interaction of treatment group and time, and shows the intervention effect (i.e. effect of depression care relative to usual care). Further, θ_i is an individual-level random effect (to allow for variation across participants) and ε_{it} is time period-specific error. With a vector of individual-level covariates X_i included in the model, we can assess main effects of patient characteristics and interactions between these X_i and indicator of treatment group. Such a model will allow us to test for significance of potential mediators: e.g., do effects of the depression care model vary by the patient's physical health at baseline? As the primary approach is intention-to-treat, the estimates will capture the average benefit for depressed patients, regardless of compliance or use of depression treatment. A secondary "completers only" analysis will be conducted as well. In addition, we will conduct a dose-response type analysis to explore the relationship between continuous implementation variables (e.g. treatment sessions attended), which are collected for all participants, and primary outcomes. Further, to better understand how or why the intervention exerted its effect, we will model the relationship

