between fidelity measures (e.g. quality) and primary outcomes, as well as conduct mediation analysis including fidelity as a mediator, in the subgroup of patients enrolled in clinics receiving the intervention arm (depression care).

Secondary Aims 1 & 2: Explore relationship of depression and depression alleviation with primary and secondary outcomes. *Hypothesis: Depression will be associated with lower adherence to each step of the PMTCT care continuum, maternal viral suppression and maternal and child health, while depression alleviation will be associated with better adherence, viral suppression and health outcomes.* We will conduct (unadjusted) bivariate analysis to initially examine significant associations between baseline depression ($EPDS \geq 13$) and depression alleviation over time with the primary and secondary outcome measures. Next, longitudinal analysis will be conducted to incorporate repeated observations of individuals and to explore the relationship between change in depression and outcomes over time, and to test whether depression alleviation ($EPDS \leq 6$) is related to change in these outcomes. Models will control for observed individual characteristics and unobservables through a random effect term to incorporate characteristics that may affect both depression and the dependent variables. However, this model does not control for simultaneity (e.g., change in viral suppression leads to lower depression). With multiple time-points, instrumental variable approaches combined with fixed effects potentially can deal with this problem, using baseline depression to predict change in depression from time 2 to time 3, if baseline depression is strongly correlated with change in depression over time. The fixed effects model will indicate important time trends in depression and the primary and secondary outcomes.

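### Baseline EPDS is collected and expected to predict the primary outcomes, but adjusting for it is not prespecified; separately, selection through peer-mother referral would go unseen without a screening log

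*Combined protocol and SAP*

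**What the plan says.** **Covariates.** In the Data analysis section, Primary Aim 1, the logistic models for adherence at each PMTCT stage and for viral suppression are described thus: "The regression models will include patient characteristics such as age, CD4 and HIV disclosure status". The repeated-measures model that follows carries an individual-level covariate vector X_i whose contents are not listed. It has a group term β for baseline differences and a group-by-time term δ, which is taken as the intervention effect.

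**Baseline depression.** Under Secondary Aims 1 & 2 the plan runs unadjusted analyses "to initially examine significant associations between baseline depression" (EPDS of 13 or more), as well as depression alleviation, and the primary and secondary outcomes. Baseline EPDS is therefore collected. The stated hypothesis is that "Depression will be associated with lower adherence to each step of the PMTCT care continuum", with viral suppression in the same sentence.

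**Design and recruitment.** The trial has "8 ANC clinics and with 400 HIV+ depressed pregnant women (50 per site"). Allocation is by clinic: "Four (4) clinics will implement usual care and 4 will implement usual care plus depression care". At all sites women are "screened for potential depression by trained peer mothers using the EPDS-2". Then, "Eligible women who express interest in participating in the study will be connected by the peer mother to the study coordinator", and the coordinator confirms eligibility and takes consent. In the rationale section, "Peer mothers will be trained to assist in depression screening and implement PST". The documents do not say when clinics are randomised relative to recruitment, and describe no concealment of the arm from those who recruit.

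**The concern.** The covariate list leaves out the one baseline variable that the plan itself singles out as related to the primary outcomes. Entry requires only a positive screen, so severity will vary among participants. With eight randomised units, the arms can readily differ in severity by chance. Enrolling more women per clinic does not remove the between-clinic part of that difference.

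If severity predicts adherence and viral suppression as hypothesised, an unadjusted comparison carries the imbalance into the arm estimate. An open list also allows covariates to be settled after results are seen.

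Recruitment is a different problem. The coordinator meets only women who have expressed interest through a peer mother. At intervention clinics the peer mother also delivers the therapy, so it is reasonable to infer that she knows the arm. If she, or the women she speaks to, respond differently because of that, the arms may differ in ways that no measured covariate captures. The documents describe no log that would reveal it.

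**Working it through.** **The plan's own figure.** 8 clinics × 50 women = 400, or 4 × 50 = 200 per arm. This reproduces. The documents give no ICC, outcome rate or effect size, so every such input below is assumed.

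**1. Chance imbalance in baseline EPDS (SD units).** For 4 versus 4 clinics of 50:

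SD of arm difference = sqrt[(2/200) × (1 + 49 × ICC)]

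| Assumed ICC | 1 + 49 × ICC | SD of arm difference | Chance of exceeding 0.2 SD, either direction | Shift at 8 points per SD |
|---|---|---|---|---|
| 0.02 | 1.98 | 0.14 | 16% | 1.1 points |
| 0.05 | 3.45 | 0.19 | 28% | 1.5 points |
| 0.10 | 5.90 | 0.24 | 41% | 1.9 points |

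The fourth column is 2 × [1 − Φ(0.2 / SD)]. The last is 8 × SD for a one-SD imbalance.

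**2. Effect on an unadjusted logistic comparison with no true arm effect.** Assume 75% adherence when EPDS is below 13 (odds 3) and a severity odds ratio of 0.5 (odds 1.5, so 60% adherence at EPDS 13 or more). Half the control arm is at EPDS 13 or more.

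- Control: 0.5 × 0.60 + 0.5 × 0.75 = 0.675.
- Intervention with 60% at 13 or more: 0.6 × 0.60 + 0.4 × 0.75 = 0.660, arm odds ratio 0.935.
- Intervention with 70% at 13 or more: 0.7 × 0.60 + 0.3 × 0.75 = 0.645, arm odds ratio 0.875.

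In 1,500 simulated trials of the 50% versus 70% case, without clustering, the unadjusted odds ratio averaged 0.876 and the 5% test rejected 10.1% of the time. With the severity indicator in the model these became 1.00 and 5.2%.

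To place these cases: if EPDS is roughly normal, 50% versus 60% is a shift of 0.25 SD, about one SD of chance imbalance at an ICC of 0.10 (0.25 / 0.24). The 50% versus 70% case is a shift of 0.52 SD, about 2.2 such SDs, so it is an extreme example.

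**3. Repeated-measures model.** A severity difference that shifts the outcome by the same amount at every time falls on β. δ is affected only if the severity effect changes over time. The logistic comparisons as described have no such baseline term.

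**4. Selection at referral.** Suppose 70% adherence, 60% of screen-positive women referred in one arm and all in the other, and a correlation of 0.1 to 0.3 between referral and underlying adherence propensity. With no true effect, the bias depends on how propensity maps to adherence:

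- logistic, propensity SD 0.5 on the logit scale: about 0.6 to 1.9 points;
- logistic, SD 1: 1.1 to 3.5 points;
- logistic, SD 2: 1.7 to 5.2 points;
- threshold model: 2.3 to 6.9 points.

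In the threshold model, with EPDS worth 8 points per SD, adjusting for baseline EPDS changes 2.3 to about 2.2 and 6.9 to about 6.6. It removes roughly 5% of the bias.

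**The case against.** The strongest reply has five parts.

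- **The list is open.** The three covariates are examples and X_i is unspecified, so a reader who infers that severity imbalance will go uncorrected goes beyond the text. This stands: what is missing is a commitment, not permission.
- **β protects the repeated-measures estimate.** This stands for a constant difference. It does not cover the stage-specific logistic models, viral suppression, or a severity effect that varies with time.
- **Chance imbalance is not bias.** Over repeated randomisations it averages to zero and belongs to the between-clinic variance, which the plan addresses through ICC sensitivity analyses. This stands. The argument for adjustment is that this trial will have one realised imbalance, and a prespecified prognostic covariate removes its measured part.
- **Recruitment has safeguards.** One instrument is used at all sites, every consenting eligible woman is to be enrolled, and the coordinator confirms eligibility and takes consent. These limit discretion. They do not cover women who never express interest to the peer mother.
- **Timing and knowledge of the arm are not stated.** A reader might infer that women are recruited after allocation by staff who all know the arm. The documents do not say so. Knowledge of the arm is a sound inference only at intervention clinics; control clinics are not addressed. The covariate point does not depend on it.

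**Conclusion.** The concern holds in two separate parts.

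First, adjustment for baseline EPDS is not prespecified, although the variable is collected and the plan expects it to predict adherence and viral suppression. On assumed ICCs of 0.02 to 0.10, the chance imbalance has an SD of 0.14 to 0.24 SD, worth 1.1 to 1.9 adherence points at an assumed 8 points per SD. That is modest, and it bears mainly on the stage-specific and viral suppression comparisons.

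Second, the route through peer mothers leaves room for selection that EPDS adjustment would hardly reduce. The documents do not fix its size or direction. The illustrations run from 0.6 to 6.9 points depending on the outcome model and the correlation, so no single figure should be quoted. A reader might suppose that adding EPDS to the model settles both parts; it does not.

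The sponsor should make both changes. Neither part shows that the primary result must be biased.

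**What to change.** **Fix 1: covariates.** Replace the open list with a closed one that includes continuous baseline EPDS in every primary model, including X_i, and state that CD4 and disclosure status are baseline values. Cost: one or two SAP sentences, with no new EPDS data collection. If the baseline score is taken after allocation, knowledge of the arm could affect it, so baseline EPDS should also be reported by arm and clinic.

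**Fix 2: recruitment.** Have peer mothers log every EPDS-2 screen and pass all consecutive screen-positive, otherwise eligible women to the existing coordinator, who makes the study offer. Report numbers screened, positive, approached and consented by clinic. State when clinics are randomised relative to recruitment and who knows the arm at that point. Cost: a short form and some coordinator time, with no new staff.

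### Statements about which patient types do well would rest on arm-by-covariate interactions picked by significance from an open list, so the false-finding risk exceeds 5% and picked effects are on average overstated

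*Combined protocol and SAP*

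**What the plan says.** All of the relevant text is in the combined protocol and SAP, Data analysis, under Primary Aim 1.

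- **Outcomes.** Logistic regression compares the arms on "PMTCT adherence, coded as a binary variable, at each stage of the PMTCT care continuum, and (ii) maternal viral suppression". The number of stages is not given.
- **Covariates.** "The regression models will include patient characteristics such as age, CD4 and HIV disclosure status that may explain variance in observed differences". Three are named, and the wording leaves the list open.
- **Interactions.** "We will also explore significant interactions between the covariates and study arm to assess which patient types are likely to be adherent and virally suppressed", comparing depression care with usual care.
- **Second model.** For the repeated-measures model the plan adds that "we can assess main effects of patient characteristics and interactions between these X_i and indicator of treatment group". The content of that covariate vector is not listed. An example follows: "do effects of the depression care model vary by the patient's physical health at baseline". This makes baseline physical health a fourth candidate.

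The document states no significance level, no multiplicity rule and no rule for reporting interactions. It does place the interactions after the arm comparison, and it makes intention to treat the primary approach.

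**The concern.** The sentence sets out a rule. Significance is the filter, and a description of patient types is the product. The set being filtered is not fixed in either direction, because both the covariates and the stages are uncounted. Two consequences follow.

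1. When many interactions are each tested at a conventional level, the chance that at least one is significant by accident is well above that level, even if the intervention works equally for everyone.
2. An interaction that is described because it passed a threshold is on average larger than the truth. The bias is greatest when power is low, and power for interactions is usually low.

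At stake is how the trial's subgroup results are read. A chance difference by age, CD4 or disclosure could be reported as a finding about who does well under depression care, and a real but modest difference could be reported at about twice its size.

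**Working it through.** **Inputs from the document.** The outline of the rationale gives the trial "at 8 ANC clinics and with 400 HIV+ depressed pregnant women (50 per site"), and "Four (4) clinics will implement usual care and 4 will implement usual care plus depression care". So 8 x 50 = 400 women, and 4 x 50 = 200 per arm. That reproduces the stated total. There is no power calculation or interaction error rate to reproduce.

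**Assumptions, because the document gives no figures.** Two-sided 5% per test; three covariates (those named); one to five primary outcomes; no true interaction; no clustering; no dropout.

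**Step 1: chance of at least one false significant interaction.** With k = covariates x outcomes independent tests, the chance is 1 - 0.95^k. For correlated outcomes, the test statistic for outcome j within a covariate was simulated as z_j = sqrt(rho) s + sqrt(1 - rho) e_j, with s and e_j standard normal and covariates independent. A hit is any |z| > 1.96.

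| Outcomes (3 covariates) | k | rho = 0 | rho = 0.8 |
|---|---|---|---|
| 1 | 3 | 1 - 0.95^3 = 14% | 14% |
| 2 | 6 | 1 - 0.95^6 = 26% (26.5%) | 22% |
| 3 | 9 | 1 - 0.95^9 = 37% | 27% |
| 5 | 15 | 1 - 0.95^15 = 54% | 34% |

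With physical health as a fourth covariate, the range is 34-46% for three outcomes and 42-64% for five. For independent tests the chance first passes one half at k = 14 (1 - 0.95^14 = 51%).

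**Step 2: size of a selected interaction.** Assume a 50/50 binary covariate, so four cells of 100 women, and 70% success in each.

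- SE of the log interaction odds ratio = sqrt(4 / (100 x 0.7 x 0.3)) = sqrt(0.190) = 0.436.
- Significance needs an odds ratio of at least exp(1.96 x 0.436) = 2.35, or at most 1/2.35 = 0.43.
- True odds ratio 1.5: ln(1.5)/0.436 = 0.93. Power = Phi(0.93 - 1.96) + Phi(-0.93 - 1.96) = 0.151 + 0.002 = 15%. The geometric mean of the significant estimates is about 2.9.
- True odds ratio 3: power about 71%, mean significant estimate about 3.7.
- True odds ratio 4: power about 89%, mean significant estimate about 4.4.

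The risk-difference scale shows the same pattern (cells of 100, reference rate 0.5 to 0.7, average arm difference 0.10, SE 0.083 to 0.099). A true interaction of 0.10 has power of 17-22% and is inflated 2.2 to 2.5 times on average when significant. A true interaction of 0.30 has power of 87-95% and is inflated 1.03 to 1.08 times, with 53-57% of the significant estimates above the truth.

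**Step 3: clustering.** In a simulation with 8 clinics of 50 and individual-level logistic regression, the interaction test held about 5% when the covariate effect was the same in all clinics. When the covariate's log-odds slope varied between clinics with an assumed SD of 0.3 or 0.5, the per-test error rose to 8-9% or 13%. Step 1 would then be too low.

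**The case against.** The strongest reply is that the plan itself says these interactions are explored. They follow the arm comparison, no subgroup hypothesis is stated, and the primary analysis is the intention-to-treat average. Family-wise control is not routinely demanded of exploratory interactions. This stands as far as it goes. It is a reason not to treat the point as a threat to the primary result, and a reason not to make formal adjustment the core of the remedy. It does not supply a fixed list, a statement that all results will be shown, or a limit on what may be concluded from a significant one.

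Several stronger readings are tempting, and the document does not support them.

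- **That a false subgroup finding is likely.** With three covariates the chance passes one half only at five outcomes with weakly correlated or independent results. The numbers of stages and covariates are not given.
- **That every selected effect is exaggerated.** Exaggeration is a property of the average. When the true interaction is large, a substantial share of the selected estimates fall below the truth.
- **That the plan later subjects these interactions to formal significance testing.** The sentence about testing for significance refers to what the plan calls mediators. Its example is a moderator, so it adds physical health as a candidate but does not set up a confirmatory test.
- **That non-significant interactions will be withheld, or that care will be targeted by subgroup.** The document says neither, and its Methods section disclaims a focus on scaling up the model.

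A further fair point is that adjustment alone does not cure exaggeration. With 15 tests the first-step threshold is 0.05/15 = 0.0033 (z = 2.94), which needs an odds ratio of at least exp(2.94 x 0.436) = 3.6. A true 1.5 that passed would be overstated even more. Reporting every estimate is what addresses this.

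**Conclusion.** The concern holds in a limited form. The plan selects arm-by-covariate interactions by significance, from an uncounted set, and turns them into statements about patient types without any limit. For the three named covariates, the chance of at least one false significant interaction runs from about 14% (one outcome) to 34-54% (five outcomes). Because adherence is analysed at each stage and viral suppression is added, more than one outcome is in play, so at least 22-27% is the relevant range. Selected interactions will be strongly overstated on average if the true ones are modest, and only mildly if they are large.

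These figures rest on an assumed two-sided 5% level, no true interaction (for the error rates), 100 women per cell and 70% success (for the odds-ratio figures), and no clustering. The primary intention-to-treat comparison is not affected. The weakness lies in how subgroup findings would be chosen and described.

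**What to change.** Replace the interaction sentence under Primary Aim 1 with wording such as:

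> Arm-by-covariate interactions will be examined for a fixed list of baseline covariates (age, CD4, HIV disclosure and physical health) for every primary outcome. All estimates will be reported with 95% CIs and the number of interactions tested, whether or not significant. They are hypothesis-generating, and no statement about which patient types benefit will rest on an unadjusted significant interaction.

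Physical health is on the list because it is the plan's own example.

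Adjusted p-values are optional. If they are shown, the plan should state the alpha and define the family as all covariate-by-outcome interactions together. Adjusting separately within each of five independent outcomes would still leave 1 - 0.95^5 = 23%. A Bonferroni rule over, say, 12 interactions (0.05/12 = 0.0042 each) gives 1 - (1 - 0.0042)^12 = 4.9%. Such a rule does not repair any per-test inflation from clinic-level variation in covariate effects, which should be acknowledged beside the table.

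The cost is one paragraph of text, one extra table, and fewer subgroup statements. No exploratory estimate is lost.

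### The named intervention effect δ (arm × time) is largely unadjusted for baseline characteristics that affect the trend, because covariates enter the repeated-measures model only as time-constant terms

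*Combined protocol and SAP*

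**What the plan says.** Under Data analysis, the Primary Aim 1 paragraph describes two analyses.

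The first is a logistic comparison of the arms on "PMTCT adherence, coded as a binary variable, at each stage of the PMTCT care continuum" and on maternal viral suppression. Directly after it comes: "The regression models will include patient characteristics such as age, CD4 and HIV disclosure status that may explain variance in observed differences".

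The second is introduced so: "We will use a repeated-measures model that will allow us to incorporate correlation in measurements of each person over time". The displayed equation contains arm (βG), a common time trend γ(t), arm × time (δ), a random effect θ for each woman and a residual error. It contains no covariate. The definitions say that "t is continuous time, G is binary indicator of treatment group", and that "δ is the interaction of treatment group and time, and shows the intervention effect". The covariates come in afterwards: "With a vector of individual-level covariates X_i included in the model, we can assess main effects of patient characteristics". In full, the terms that this sentence lists are "main effects of patient characteristics and interactions between these X_i and indicator of treatment group". The covariates carry the subscript i and no t. Neither a covariate × time term nor a covariate × arm × time term is written, and the link function is not stated.

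On timing, the Methods say the study will enrol eligible women and "survey them at baseline, month 6, 12 and 18 following delivery". Women who miscarry have a final survey 6 months afterwards.

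**The concern.** A covariate that is constant within a woman can explain why her adherence is high or low on average. It cannot explain why it rises or falls. In this model β carries the arm difference in level and δ the arm difference in trend. Main effects and covariate × arm terms therefore act on β, while the effect that will be read as the result is δ.

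Only 8 clinics are allocated, 4 to each arm, so patient mix may differ between arms by chance. If a characteristic that differs also predicts how adherence changes through pregnancy and the 18 months after delivery, the difference passes into δ. A longer list of main effects would give little protection. A reader who sees covariates in the model could nevertheless take δ to be adjusted for them.

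**Working it through.** The plan gives no figure to reproduce here. The check is algebra first, then simulation.

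**Inputs from the document:** 8 clinics × 50 women = 400; binary adherence; continuous time; surveys at baseline and at 6, 12 and 18 months after delivery; a random effect per woman; X_i as main effects and X_i × arm. **Everything else below is assumed.**

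**Step 1: algebra for the displayed (additive) form.** With covariates,

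y_it = α + βG_i + γ(t) + δG_i·t + κX_i + ηX_iG_i + θ_i + ε_it.

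Subtract each woman's own mean, with common visit times and complete data:

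y_it − ȳ_i = [γ(t) − γ̄] + δG_i(t − t̄) + (ε_it − ε̄_i).

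The κ and η terms have gone. The woman means contain δ only through (β + δt̄)G_i. Because t̄ is the same for every woman, they cannot separate δ from β. All information on δ is within-woman, so its estimate is identical with or without κ and η. If the truth also contains λX_i·t, the estimate targets δ + λΔ, where Δ is the arm difference in mean X.

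**Step 2: does this hold outside the exact case?** Simulation with 400 women, 4 visits and 60 replicates per scenario. Assumed: true δ = 0.30 per year, Δ = 0.4 SD, λ = 0.4 per year, X effect on level 0.8, random-intercept SD 1. Step 1 predicts 0.30 + 0.4 × 0.4 = 0.46 without an X × t term.

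| Model and data | δ, no X | δ, X and X × arm | Mean absolute change | SD of δ (no X) | δ, X and X × t |
|---|---|---|---|---|---|
| Linear, common visits, complete | 0.457 | 0.457 | 0.000 | 0.079 | 0.295 |
| Linear, individual visits, complete | 0.470 | 0.470 | 0.002 | 0.068 | 0.307 |
| Linear, common visits, dropout | 0.431 | 0.438 | 0.014 | 0.100 | 0.289 |
| Linear, individual visits, dropout | 0.454 | 0.464 | 0.015 | 0.087 | 0.313 |
| Random-intercept logistic, common visits, complete | 0.416 | 0.416 | 0.002 | 0.157 | 0.324 |
| Random-intercept logistic, individual visits, complete | 0.398 | 0.396 | 0.007 | 0.198 | 0.300 |
| Random-intercept logistic, common visits, dropout | 0.410 | 0.427 | 0.028 | 0.185 | 0.339 |
| Random-intercept logistic, individual visits, dropout | 0.363 | 0.385 | 0.034 | 0.217 | 0.294 |

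The first row is exact in every replicate. Elsewhere the mean change is small beside the sampling SD, although the largest single change was 0.13 (logistic with dropout). Under dropout the time-constant terms moved the average further from 0.30, not nearer. Adding X × t removed most or all of the excess.

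**Step 3: size in percentage points.** A second simulation used a linear random-intercept fit to binary data for 400 women, with 1,500 runs per scenario. Assumed: visits at 0, 12, 18 and 24 months, latent correlation 0.6, no clinic effect and no true arm effect. The expected bias over follow-up is the imbalance times the extra loss.

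| Share with X, by arm | Extra loss in X (points) | Product (points) | δ, no X | δ, X main effect | δ, X and X × t | Rejection rate without X × t |
|---|---|---|---|---|---|---|
| 40% v 50% | 20 | 0.10 × 20 = 2.0 | −1.99 | −1.99 | 0.03 | 7.6% |
| 40% v 55% | 25 | 0.15 × 25 = 3.75 | −3.85 | −3.85 | 0.06 | 12% |
| 40% v 60% | 30 | 0.20 × 30 = 6.0 | −5.95 | −5.95 | 0.05 | 24% |

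With X × t the rejection rate was 4.4% to 5.2%. A small check of 12 runs with 10% dropout per visit gave −3.53 points without X, −3.51 with the main effect and 0.01 with X × t.

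**Step 4: how likely are these imbalances?** If X were independent between women, with 200 per arm, the standard error for 40% v 50% is √(0.40 × 0.60/200 + 0.50 × 0.50/200) = 0.049. The three imbalances are then about 2, 3 and 4 standard errors. Clustering of X by clinic would make them less extreme, but the document gives no figure for it.

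**The case against.** Three stronger readings are tempting, and the document supports none of them.

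- A reader might infer that covariates enter as main effects alone. The same sentence adds covariate × arm interactions. These are also constant within a woman, so the conclusion for δ is the same.
- A reader might infer that the covariates cannot alter δ at all. That is exact only for a linear model with common visit times and complete data. Here the outcome is binary and the link unstated, follow-up is timed from delivery while baseline falls in pregnancy, and miscarriage shortens some series. δ will move, usually by little. A pooled logistic model moved more (mean 0.06 to 0.08), but it omits the woman-level random effect that the plan specifies.
- A reader might infer that the primary outcomes have no adjusted analysis. The logistic arm comparisons do include patient characteristics, and there main effects do adjust the arm contrast. The statement about age, CD4 and disclosure belongs to that comparison; the plan does not expressly promise an adjusted δ.

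It can also be said that the text is compressed. It asks whether the effect of depression care varies with physical health at baseline. If δ is the effect, that needs a covariate × arm × time term, which would normally bring covariate × time with it. This is fair as a guess at intent, but the terms listed stop at covariate × arm.

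Finally, the rejection rates in Step 3 fix the imbalance in one direction in every run. They are conditional on that imbalance and are not the trial's type I error, since before allocation the imbalance could fall either way. This objection stands in full.

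**Conclusion.** The point holds for δ in the repeated-measures model. As written, its covariate terms adjust level and leave the arm difference in trend exactly or nearly unadjusted. The exact result rests only on the additive random-intercept form with common visits and complete data. That the change is otherwise slight rests on simulation under assumed values.

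The bias is approximately the covariate imbalance times the covariate's effect on slope, and it is zero if either is zero. The sizes of 2 to 6 points are illustrative, because neither factor is given in the document; the larger ones need large imbalances. This is a cheap and worthwhile improvement, and does not show that the trial's result will be biased.

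**What to change.** In the Primary Aim 1 paragraph:

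1. Replace the open-ended examples with a prespecified list of covariates measured at baseline, for example age, CD4 and HIV disclosure status. Baseline measurement matters for disclosure, because the Secondary aim also lists it as a possible mediator.
2. Add an X_i × t term for each listed covariate to the repeated-measures model, beside its main effect.
3. State that the adjusted δ is reported from that model.

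The same edit should name the link function and say whether δ or the adjusted logistic arm comparison is the primary estimate, since the paragraph leaves both open.

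The cost is a few sentences, one degree of freedom per single-term covariate and a little more analysis work. No new data are needed.
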